2.4.4 Intra-tumoral immune infiltrate

Sunitinib has been shown in preclinical models and in patients to favorably alter the immune cell environment through promotion of a T-helper 1 phenotype, reduction in T-regulatory cells and reduction in myeloid derived suppressor cells.^{117,118,140,141} The contribution of these observations to the antitumor mechanism of sunitinib is unclear at present. Where fresh tissue is available, we propose to analyze immune subsets including but not limited to CD8, CD4, CD56, CD68 by multiparametric flow cytometry in the [name] laboratory, DTB, NCI.

3 PATIENT SELECTION

3.1 ELIGIBILITY CRITERIA

- 3.1.1 Histological confirmation of thymoma (Group 1 only) or thymic carcinoma by the pathology department/CCR/NCI or the pathology department of participating institutions.
- 3.1.2 At least one prior line of platinum-based chemotherapy or patient must have refused

cytotoxic chemotherapy. Progressive disease must be documented prior to study entry.

- 3.1.3 Patients must not have received chemotherapy, radiation therapy, or undergone major surgery within 4 weeks prior to enrollment.
- 3.1.4 Patients must have measurable disease, per RECIST 1.1. See Section 12 for the evaluation of measurable disease.
- 3.1.5 Age ≥ 18 years
- 3.1.6 ECOG performance status ≤ 2 (Karnofsky $>50\%$, see Appendix A).
- 3.1.7 Life expectancy of greater than 3 months
- 3.1.8 Patients must have normal organ and marrow function as defined below:
- | | |
|-----------------------------|--|
| - hemoglobin | ≥ 9 g/dL |
| - leukocytes | $\geq 3,000$ /mcL |
| - absolute neutrophil count | $\geq 1,200$ /mcL |
| - platelets | $\geq 100,000$ /mcL |
| - total bilirubin | within normal institutional limits |
| - serum calcium | ≤ 12.0 mg/dL |
| - AST(SGOT)/ALT(SGPT) | $\leq 2.5 \times$ institutional upper limit of normal* |
| - creatinine | within normal institutional limits |
- OR
- | | |
|--|--|
| - creatinine clearance | ≥ 60 mL/min/1.73 m ² for patients with creatinine levels above institutional normal. |
| - * If subjects have liver metastases, both ALT and AST must be $\leq 5 \times$ ULN. | |
| - Patients must have QTc < 500 msec | |
- 3.1.9 PT or INR, and APTT $\leq 1.5 \times$ upper limit of normal (ULN), unless the abnormality can be explained by the presence of lupus anticoagulant or if these values are in the therapeutic range for a patient on low molecular weight heparin.
- 3.1.10 The following groups of patients are eligible provided they have New York Heart Association Class II (NYHA; see Appendix B) cardiac function on baseline ECHO/MUGA:
- those with a history of Class II heart failure who are asymptomatic on treatment
 - those with prior anthracycline exposure
- those who have received central thoracic radiation that included the heart in the radiotherapy port.
- 3.1.11 Patients must have blood pressure (BP) no greater than 140 mmHg (systolic) and 90

mmHg (diastolic) for eligibility. Initiation or adjustment of BP medication is permitted prior to study entry provided that the average of three BP readings at a visit prior to enrollment is less than 140/90 mmHg.

- 3.1.12 Absence of brain metastases as confirmed by imaging of the brain by MRI or CT brain with contrast performed at baseline screening.
- 3.1.13 The effects of sunitinib on the developing human fetus at the recommended therapeutic dose are unknown. For this reason and because anti-angiogenic agents are known to be teratogenic, women of childbearing potential and men must agree to use adequate contraception (hormonal or barrier method of birth control; abstinence) prior to study entry and for the duration of study participation. All women of childbearing potential must have a negative pregnancy test prior to receiving sunitinib. Should a woman become pregnant or suspect she is pregnant while participating in this study, she should inform her treating physician immediately. Men treated or enrolled on this protocol must also agree to use adequate contraception prior to the study, for the duration of study participation, and 4 months after completion of sunitinib administration.
- 3.1.14 Ability to understand and willingness to sign a written informed consent document.

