5.3 DURATION OF THERAPY

In the absence of treatment delays due to adverse event(s), treatment may continue until one of the following criteria (off treatment criteria) applies:

- Disease progression,
- Intercurrent illness that prevents further administration of treatment,
- Unacceptable adverse event(s),
- Delay of treatment of ≥ 3 weeks,
- Positive pregnancy test
- Patient decides to withdraw from the study, or
- General or specific changes in the patient's condition render the patient unacceptable for further treatment in the judgment of the investigator.

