5.4 DURATION OF FOLLOW UP

Prior to documenting removal from the study, effort must be made to have all subjects complete a safety visit approximately 30 days following the last dose of study therapy; then patients will be followed either with clinic visits or phone interviews yearly until death. Patients removed from treatment for unacceptable adverse event(s) will be followed clinically until resolution or stabilization of the adverse event, and then via clinic visits or phone interviews yearly until death.

The following information will be collected:

- Date of follow up
- Is patient dead or alive?
- If dead, document exact date of death.
- Further treatment(s), if any
- Document date of disease progression

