5.5 CRITERIA FOR REMOVAL FROM STUDY

5.5.1 Once a patient has been removed from study, no further data can be collected; therefore, with completion of the duration of follow-up described in Section 5.4, the criteria for removal from study are:

- Lost to follow-up
- Death, or
- The patient decides to withdraw from the study.

The reason for study removal and the date the patient was removed must be documented in the database.

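### Minor safety point: 3.1.13 gives men a contraception interval after sunitinib but ties women to study participation only, so a woman who withdraws from the whole study soon after a dose has no stated cover

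*Combined protocol and SAP*

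**What the plan says.** Section 3.1.13 explains why contraception is required: "The effects of sunitinib on the developing human fetus at the recommended therapeutic dose are unknown", and it regards anti-angiogenic agents as teratogenic. It then sets two periods.

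- Women of childbearing potential, and men, must use contraception "prior to study entry and for the duration of study participation".
- A later sentence, for men only, requires it before the study, "for the duration of study participation, and 4 months after completion of sunitinib administration".

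The instruction to report a pregnancy also applies only while a woman is taking part in the study. Elsewhere, 3.2.9 and 18.1 exclude pregnant women and 5.3 stops treatment on a positive pregnancy test. No section in the review copy gives women an interval after the last dose.

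Three sections decide when participation ends.

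- 5.3 lists "Patient decides to withdraw from the study" as a reason to stop treatment.
- 5.5.1 lists "The patient decides to withdraw from the study" as a reason for removal from study, alongside death and loss to follow-up, and states: "Once a patient has been removed from study, no further data can be collected".
- 5.4 says that, before removal is documented, "effort must be made to have all subjects complete a safety visit approximately 30 days following the last dose of study therapy". Long-term contact comes after that visit and has no fixed end short of death: the patients stay in yearly follow-up by clinic or telephone.

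**The concern.** The men's duty has an end point counted from the drug. The women's duty has an end point counted from study status. The two agree only if a woman stays on study until the drug has cleared. Because patient withdrawal ends both treatment and participation, a woman can leave while sunitinib and its active metabolite are still present, and at that moment 3.1.13 asks nothing more of her.

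At stake is a possible conception during residual exposure to a drug that the protocol itself treats as a fetal hazard. The protocol gives no reason for setting a post-dose interval for men and none for women, whose exposure is direct. This is a participant-safety point and does not touch the endpoints.

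**Working it through.** **Step 1. Who is covered.** Reading 3.1.13 with 5.3, 5.4 and 5.5.1:

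| Situation | Participation ends | Contraception required during washout? |
|---|---|---|
| Woman stops drug, stays in follow-up | At death, loss to follow-up or later withdrawal | Yes |
| Woman withdraws from the whole study, completes the 30-day visit before removal is documented | About day 30 | Arguably yes, by implication |
| Woman withdraws from the whole study, declines the visit | At withdrawal | No |
| Man, any of these | Not relevant | Yes, 4 months after sunitinib |

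The gap is the third row, and the second row so far as the implied cover is not explicit.

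**Step 2. How long exposure lasts.** The plan states no washout for women, so there is no figure to reproduce. The inputs come from 2.2.5.4: terminal half-lives of 40-60 h for sunitinib and 80-110 h for SU012662, the active metabolite. The phase 1 dose-escalation study described there gives 41-86 h at the recommended dose, which I use as the upper bound for parent drug. The five-half-life rule (a fall to 1/32) is my assumption.

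Days = 5 × half-life in hours / 24.

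- Sunitinib: 5 × 40 / 24 = 8.3 days; 5 × 60 / 24 = 12.5 days.
- Sunitinib at 86 h: 5 × 86 / 24 = 17.9 days.
- SU012662: 5 × 80 / 24 = 16.7 days; 5 × 110 / 24 = 22.9 days.

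A Group 2 patient who withdraws at the end of her rest week has already used 7 of those days. That leaves 16.7 − 7 = 9.7 to 22.9 − 7 = 15.9 days for the metabolite.

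**Step 3. Fraction of metabolite remaining, simple decline.** Fraction = 0.5^(hours / half-life), at 80 h and 110 h:

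| Day after last dose | 80 h | 110 h |
|---|---|---|
| 7 | 23% | 35% |
| 14 | 5% | 12% |
| 28 | 0.3% | 1.4% |
| 30 | 0.2% | 1.1% |

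**Step 4. Allowing for metabolite still being formed from parent drug.** Assume steady state at the last dose. With kp and km equal to ln 2 divided by the parent and metabolite half-lives,

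M(t)/Mss = e^(−km·t) + [km/(km − kp)] × (e^(−kp·t) − e^(−km·t)).

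| Parent / metabolite half-life | Day 7 | Day 14 | Day 28 | Falls to 1/32 at |
|---|---|---|---|---|
| 40 h / 80 h | 41% | 11% | 0.6% | 20 days |
| 60 h / 110 h | 59% | 24% | 3.1% | 28 days |
| 86 h / 110 h | 66% | 31% | 5.1% | about 31 days |

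The steady-state assumption is slightly generous. Section 2.3.2 says steady state is reached in 2 weeks, but 14 days of dosing bring the metabolite to 1 − 0.5^(336/80) = 95% or 1 − 0.5^(336/110) = 88% of it. The last row pairs the longest parent value with the longest metabolite value, so it is an extreme.

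**The case against.** The strongest reply is that this is a narrow case, already partly handled. Follow-up runs until death, so for a woman who stays on study the duty outlasts any washout. For a woman who leaves, 5.4 asks for an effort to hold a visit at about day 30 before removal is documented, and it applies to all subjects. Where that visit takes place, participation reaches past the 17 to 23 days for the metabolite and past the modelled 20 to 28 days. This stands, and it shrinks the gap considerably. It does not close it: the visit is best effort, a withdrawing patient can decline it, and it carries no contraception duty.

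A reader might infer three stronger things that the documents do not support.

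- **That women in general lack cover after stopping sunitinib.** They do not; 5.4 and 5.5.1 keep them in the study.
- **That drug and metabolite both persist for 3 to 4 weeks.** Five half-lives of sunitinib take 8 to 13 days, or 18 at 86 h. The 4-week figure is for the metabolite and depends on the model in Step 4.
- **That women are given no such instruction anywhere.** The consent pages were removed from the review copy and may contain one. The point concerns the protocol criterion only.

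It is also fair to say that the percentages measure residual drug and not fetal risk, for which the documents give no exposure threshold. A change to an eligibility criterion reaches only new entrants unless women on treatment are told separately. Section 17.2 expected about one further year of Group 2 accrual after the 2014 amendment, and this version is dated April 2020. Current enrolment is not stated.

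**Conclusion.** The point holds as a minor one. As written, 3.1.13 lets a woman who withdraws from the whole study within about 3 weeks of a dose stop contraception while active metabolite is likely still present. The window is 17 to 23 days on five metabolite half-lives and about 4 weeks if formation from parent is counted, with 31 days as the extreme.

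This rests on the half-lives in 2.2.5.4, on the assumed five-half-life rule and, for the longer figures, on steady state at the last dose. The number affected would be very small: Group 2 is capped at 15 patients, and the documents give no count of women of childbearing potential and no withdrawal rate. Nothing in the sample size or the analysis depends on it.

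**What to change.** Add one sentence to 3.1.13: *Women of childbearing potential must also agree to use adequate contraception for at least 5 weeks after the last dose of sunitinib, including if they withdraw from treatment or from the study.*

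Five weeks is 35 days, which exceeds the 31-day extreme and also seven metabolite half-lives at 110 h (7 × 110 / 24 = 32.1 days). The sponsor may choose a longer interval; the men's 4 months would be simple, though the documents do not derive that figure for women. The agreement should be made at entry, because 5.5.1 allows no data collection after removal. Give the same instruction to any women still on drug, since an amended eligibility criterion would not otherwise reach them.

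The cost is a slightly longer obligation for very few women, which cannot be monitored after withdrawal.

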3.2 EXCLUSION CRITERIA

- 3.2.1 Patients with tumor amenable to potentially curative therapy.
- 3.2.2 Prior treatment within the past 6 months with sunitinib, sorafenib, bevacizumab or other multikinase inhibitors targeting any of the following: vascular endothelial growth factors 1–3 (VEGF1–3), FMS-like tyrosine kinase 3 (FLT3), stem cell growth factor (c-KIT), platelet-derived growth factors- α and - β (PDGF- α , - β), colony-stimulating factor 1 (CSF1), and the ‘RET’ receptor for glial-derived neurotrophic factors.
- 3.2.3 Patients with symptomatic brain metastases will be excluded from trial secondary to poor prognosis. However, patients who have had treatment for their brain metastasis and whose brain disease has remained stable for 3 months without steroid therapy may be enrolled.
- 3.2.4 Patients with evidence of severe or uncontrolled systemic disease, or any concurrent condition, which could compromise participation in the study, including, but not limited to, active or uncontrolled infection, immune deficiencies, uncontrolled HBV and/or HCV infection unless sustained virologic response to HCV therapy, uncontrolled diabetes, serious non-healing ulcer, wound or bone fracture, history of intra-abdominal abscess, abdominal fistula or gastrointestinal perforation within 28 days of treatment, history of pulmonary embolism in the past 12 months, uncontrolled hypertension, myocardial infarction, cardiac arrhythmia, stable/unstable angina, symptomatic congestive heart failure, or coronary/peripheral artery bypass graft or stenting within 12 months prior to

study entry, Class III or IV heart failure as defined by the NYHA functional classification system (see [Appendix B](#)), stroke/cerebrovascular accident or transient ischemic attack within the past 12 months or psychiatric illness/social situations which would jeopardize compliance with the protocol.

- 3.2.5 History of a previous invasive malignancy within the last 5 years, except adequately treated non-melanoma skin cancer, papillary carcinoma of the thyroid or carcinoma in situ of the uterine cervix.
- 3.2.6 Patients who have had chemotherapy or radiotherapy within 4 weeks (6 weeks for nitrosoureas or mitomycin C) prior to entering the study or those who have not recovered from adverse events due to agents administered more than 4 weeks earlier.
- 3.2.7 Patients who are receiving any other investigational agents.
- 3.2.8 History of allergic reactions attributed to compounds of similar chemical or biologic composition to sunitinib.

Patients receiving any medications or substances that are strong inhibitors or inducers of CYP3A4 are ineligible. (A list of potent CYP3A4 inducers or inhibitors can be found in Section 5.2) An exception will be made for patients who are on ritonavir-based highly active antiretroviral therapy, in which case the starting dose of sunitinib will be modified as indicated in Sections 5.2.11. Every effort should be made to switch patients taking such agents or substances to other medications. A comprehensive list of medications and substances known or with the potential to alter the pharmacokinetics of sunitinib through CYP3A4 is provided in [Appendix C](#).

- 3.2.9 Pregnant women are excluded from this study because sunitinib angiogenesis inhibitor with the potential for teratogenic or abortifacient effects. Because there is an unknown but potential risk for adverse events in nursing infants secondary to treatment of the mother with sunitinib breastfeeding should be discontinued if the mother is treated with sunitinib.
- 3.2.10 Patients who require therapeutic doses of Coumadin derivative anticoagulants such as warfarin are excluded. Low molecular weight heparin is permitted, provided the patient's PT/INR is ≤ 1.5 . Coumadin doses of up to 2 mg daily are permitted for prophylaxis of thrombosis.
- 3.2.11 Patients with a pre-existing thyroid abnormality who are unable to maintain thyroid function in the normal range with medication are ineligible.
- 3.2.12 Patients with any condition (e.g., gastrointestinal tract disease resulting in an inability to take oral medication or a requirement for IV alimentation, prior surgical procedures affecting absorption, or active peptic ulcer disease) that impairs their ability to swallow

and retain sunitinib tablets are excluded.

3.2.13 Patients with QTc prolongation (defined as a QTc interval equal to or greater than 500 msec) or other significant ECG abnormalities are excluded.

3.2.14 Patients with poorly controlled hypertension (systolic blood pressure of 140 mmHg or higher or diastolic blood pressure of 91 mmHg or higher) are ineligible.

3.2.15 Patients who require use of therapeutic doses of coumarin-derivative anticoagulants such as warfarin are excluded, although doses of up to 2 mg daily are permitted for prophylaxis of thrombosis. Note: Low molecular weight heparin is permitted provided the patient's PT INR is ≤ 1.5 .

3.2.16 Patients with HIV infection are eligible provided their CD4 count is greater than or equal to the institutional LLN (≥ 334 cells/uL).

3.3 INCLUSION OF WOMEN AND MINORITIES

Both men and women of all races and ethnic groups are eligible for this trial.

Accrual Targets					
Ethnic Category	Sex/Gender				
	Females		Males		Total
Hispanic or Latino	3	+	3	=	6
Not Hispanic or Latino	26	+	26	=	52
Ethnic Category: Total of all subjects	29 (A1)	+	29 (B1)	=	58 (C1)
Racial Category					
American Indian or Alaskan Native	2	+	2	=	4
Asian	5	+	5	=	10
Black or African American	4	+	4	=	8
Native Hawaiian or other Pacific Islander	1	+	1	=	2
White	17	+	17	=	34
Racial Category: Total of all subjects	29 (A2)	+	29 (B2)	=	58 (C2)

(A1 = A2)

(B1 = B2)

(C1 = C2)

Accrual Rate: 3 patients/month

Total Expected Accrual: 41 Min 58 Max

4 REGISTRATION PROCEDURES

4.1 COORDINATING CENTER

Authorized staff must register an eligible candidate with NCI Central Registration Office (CRO) within 24 hours of signing consent. A registration Eligibility Checklist from the web site (<http://home.ccr.cancer.gov/intra/eligibility/welcome.htm>) must be completed and sent via encrypted email to: NCI Central Registration Office [contact]. After confirmation of eligibility at Central Registration Office, CRO staff will call pharmacy to advise them of the acceptance of the patient on the protocol prior to the release of any investigational agents. Verification of Registration will be forwarded electronically via e-mail to the research team. A recorder is available during non-working hours.

4.2 PARTICIPATING SITE

All patients must be registered through the NCI Central Registration Office (CRO). The CRO is open from 8:30am to 5:30pm EST Monday through Friday, excluding federal holidays. A protocol registration form will be supplied by the CCR study coordinator and updates will be provided as needed. Subject eligibility and demographic information is required for registration. To initially register a subject after the participant has signed consent, complete the top portion of the form and send to CCR study coordinator. Once eligibility is confirmed, complete the remainder of the form which is the eligibility checklist and send to CCR study coordinator. In addition, source documents supporting the eligibility criteria must be sent to the CCR study coordinator. The CCR study coordinator will notify you either by e-mail or fax that the protocol registration form has been received which will include the unique patient/subject ID number. Questions about eligibility should be directed to the CCR study coordinator or PI. Questions related to registration should be directed to the CCR study coordinator.

Technical questions about the form should be directed to the Central Registration: Office [contact]).

4.3 TREATMENT INITIATION TIMELINE

Following registration, patients should begin protocol treatment within 5 days. Issues that would cause treatment delays should be discussed with the Principal Investigator. If a patient does not receive protocol therapy within 5 days following registration, the patient may have to be removed from study. The Lead Associate Investigator should be notified of treatment initiation delays as soon as possible.

5 TREATMENT PLAN

5.1 AGENT ADMINISTRATION

Sunitinib will be administered on an outpatient basis. Reported adverse events and potential risks are described in Section 7. Appropriate dose modifications are described in Section 6. No investigational or commercial agents or therapies other than sunitinib may be administered with

the intent to treat the patient's malignancy.

- 5.1.1 For Group 1, sunitinib will be administered orally at a dose of 50 mg daily for 4 consecutive weeks followed by 2 weeks of rest with no sunitinib, every 6 weeks (4/2 schedule). For Group 2, sunitinib will be administered orally at a dose of 50 mg daily for 2 consecutive weeks followed by 1 week of rest with no sunitinib, every 3 weeks (2/1 schedule). Patients should be instructed to store sunitinib at room temperature. Patients will take sunitinib once daily, with or without food, as desired. Patients should be advised to drink plenty of water or take rehydration fluids to avoid dehydration if diarrhea occurs.
- 5.1.2 Because hypertension is a known and potentially serious but rare adverse event associated with sunitinib maleate treatment, patients will have their blood pressure monitored and recorded at baseline and weekly during treatment including the weeks off the investigational drug either at the doctor's office or using any calibrated electronic device (such as those found at a local drug store or pharmacy). [Appendix D](#) and [Appendix F](#) detail the collection and recording of blood pressure related information.
- 5.1.3 Baseline assessment of cardiac function (ECHO/MUGA) is required for all patients. Routine monitoring for cardiac function (ECHO/MUGA) should be performed at baseline and then every other cycle of treatment in the following groups of patients: (1) those entering the trial with NYHA Class II cardiac dysfunction (see [Appendix B](#)), (2) those with a history of Class II heart failure who are asymptomatic on treatment, and (3) in those previously exposed to anthracyclines or thoracic irradiation if the heart was included in the radiotherapy port.
- 5.1.4 Although adrenal gland insufficiency is rarely seen with sunitinib treatment, patients should be clinically followed for the signs and symptoms of this complication, especially (1) patients with co-morbidities associated with adrenal dysfunction, (2) patients with pre-existing adrenal insufficiency (primary or secondary), and (3) patients with concomitant stress (e.g., fever, infection, bleeding, serious accident, surgery) that may precipitate overt adrenal insufficiency in the presence of subclinical sunitinib-induced adrenal toxicity. If clinically indicated, objective testing for adrenal gland function should be conducted.
- 5.1.5 Patients with bulky solid tumors should be monitored closely for pneumothorax, intestinal fistulae, or intestinal perforation in the event of rapid tumor destruction.
- 5.1.6 Patients should be alerted to the possibility that sunitinib capsules can cause a yellow discoloration of the skin on direct contact. If this happens, the patient should wash immediately with soap and water.
- 5.1.7 Patients will be requested to maintain a medication diary of each dose of medication. The medication diary will be returned to clinic staff at the end of each course.

- 5.1.8 Thyroid function (free T4 and TSH) will be monitored at baseline and subsequently every 6 weeks (2 cycles).

